11.2 End of Study Treatment Visit

End of study visit will be conducted within 30-45 days of last cycle of therapy

- Physical Examination
- Vital signs
- Height and weight
- Concomitant medication documentation, including over the counter medication and supplements
- CBC with differential
- Serum chemistry panel as mentioned above
- LDH
- Pregnancy test for females of childbearing potential
- ECOG performance status (not required if patient has disease progression)
- Adverse event evaluation

- Diagnostic CT of neck, chest, abdomen, pelvis with IV and oral contrast and PET scan to be done between 30-45 days after the last cycle of therapy. Neck CT can be omitted at the discretion of the investigator if there was no involvement at baseline. If unable to obtain both CT and PET scan due to insurance restrictions, either CT or PET are acceptable, but PET scan is preferred
 - For patients coming off treatment due to disease progression, scans are only required, if the last scan within 60 days did not show disease progression. If the patient had a scan within the last 60 days that document progression, no further scans are needed.
- BM biopsy to be repeated between 30-45 days after the last cycle of therapy if it was positive prior to start of the study drug.
 - BM biopsy may be omitted for patients who are coming off treatment due to disease progression.

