11.3 Duration of Follow Up

As stated in section 6.7.2 after completion of the study the subjects will be followed for a total of 3 years. The follow up visits will be done at 6, 12, 24 and 36 months after the last cycle of therapy and will include:

- Physical Examination
- Vital signs, height, and weight
- CBC with differential
- Serum chemistry panel as mentioned above
- LDH
- ECOG performance status
- Adverse events evaluation (only the adverse events attributed to the study drug)
- CT scans - neck, chest, abdomen and pelvis with IV and oral contrast to be done at 6, 12, and 24 months after the last cycle of therapy if no progressive disease. Neck CT can be omitted at the discretion of the investigator if there was no involvement at baseline

If the patient is unable to follow up with the local site in person, virtual visits may be used to capture applicable procedures during long-term follow up only. If a virtual visit is completed in follow up every attempt should be made to complete the required assessments listed above, though if they are not completed it will not be considered a protocol deviation.

Patients who have progressive disease or start a new treatment are not required come in for clinical follow ups. These patients can be contacted over the phone by the study personnel to obtain the following information

- Disease status
- Adverse event evaluation only if patients have residual persistent symptoms related to BV treatment
- Current lymphoma treatment

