- b. Bone marrow biopsy only if positive prior to start of the study drug
- c. Pregnancy test to be done within 72 hours of starting the study drug

- d. Restaging CT scans not required if disease has progressed
- e. CD30 status to be assessed by the site enrolling the patient
- f. Tumor biopsy slides should be sent to CCF for correlative studies within 4 weeks of the start of the treatment
- g. Bone marrow biopsy only if evidence of involvement previously, and/or suspicion of involvement at the time of current relapse.
- h. For Cycles 18 and beyond, scans are to be done every six months +/- two weeks.
- i. Only adverse events attributed to the study drug
- j. CT neck can be omitted at baseline if the investigator feels there is no or low suspicion for involvement
- k. These labs do not need repeated on C1D1 if they were performed at baseline within 72 hours of start of study treatment
- l. Height is only required at screening.
- m. Long term follow up visits may be completed via virtual visit if necessary. Every attempt should be made to complete the assessments although if they are not completed this is not considered a protocol deviation.

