12.0 MEASUREMENT OF EFFECT

12.1 Antitumor Effect

Response will be assessed using CT scans according to the revised Cheson Criteria [1]. Please see section 11.4 for the schedule of the imaging studies. Patients will have pre-treatment and end of treatment FDG-PET and/or CT to monitor their response to treatment. Interim response will be assessed after cycle 4 and 10 using CT scans. During follow up patients will have CT scans done at 6, 12, and 24 months after the last cycle of therapy.

All patients will be evaluable for toxicity from the time of their first treatment with Brentuximab Vedotin

The following guidelines are to be used for establishing tumor measurements at baseline and for subsequent comparison:

- The six largest dominant nodes or extranodal masses must be identified at baseline.
- If there are 6 or fewer nodes and extranodal masses, all must be listed as dominant.

If there are more than 6 involved nodes or extranodal masses, the 6 largest dominant nodes or extranodal masses should be selected according to the following features:

- nodes should be clearly measurable in at least two perpendicular measurements
- nodes should be from as disparate regions of the body as possible
- nodes should include mediastinal and retroperitoneal areas of disease whenever these sites are involved.
- Measurements for all dominant nodes and extranodal masses will be reported at baseline. Measurements on non-dominant nodes are not required. The lymph nodes or extranodal masses selected for measurement should be measured in two perpendicular diameters, one of which is the longest perpendicular diameter. The lymph nodes should be measured in centimeters to the nearest one tenth of a centimeter (e.g. 2.0 cm, 2.1cm, 2.2 cm, etc.)
- The two measured diameters of each lymph node site or extranodal mass should be multiplied giving a product for each nodal site or extranodal mass. The

product of each nodal site should be added, yielding the sum of products of the diameters (SPD). The SPD will be used in determining the definition of response for those who have less than a complete response.

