12.2.2.2 Progression Free Survival

Progression-free survival (PFS) is defined as the time from enrollment into the study to disease progression or death due to any cause. The distribution of PFS will be estimated using the Kaplan-Meier method. Disease progression may be defined as the date of documentation of a new lesion or enlargement of a previous lesion, or the date of the scheduled clinic visit immediately after radiologic assessment has been completed. For a patient who is alive without progression at the end of study follow-up, observation of PFS is censored on the date of last contact.

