12.2.2.3 Overall Survival

The OS is defined as the time from enrollment to the time of death due to any cause. For a patient who is alive at the end of study follow-up, observation of OS is censored on the date of last contact. The distribution of OS will be estimated using the Kaplan-Meier method.

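### PFS is censored at last contact, as OS is, although contact can happen without imaging; the upward bias is small and the censoring sentence in 12.2.2.2 should be tied to disease assessment

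*Combined protocol and SAP*

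**What the plan says.** Section 12.2.2.2 defines PFS from enrollment to progression or death from any cause. For a patient who is "alive without progression at the end of study follow-up, observation of PFS is censored on the date of last contact". Section 12.2.2.3 has the parallel rule: "For a patient who is alive at the end of study follow-up, observation of OS is censored on the date of last contact". Section 14.0 estimates both by Kaplan-Meier. Section 12.2.2.2 dates progression either by documentation of a new or enlarged lesion, or by the scheduled clinic visit that follows the radiologic assessment.

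The assessment schedule is set elsewhere:

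- Section 11.2, end of treatment: "Diagnostic CT of neck, chest, abdomen, pelvis with IV and oral contrast and PET scan to be done between 30-45 days" after the last cycle.
- Section 12.1: "During follow up patients will have CT scans done at 6, 12, and 24 months after the last cycle of therapy".
- Section 11.3: "The follow up visits will be done at 6, 12, 24 and 36 months after the last cycle of therapy". The calendar in 11.4 shows no CT at 36 months.
- Section 11.3: "virtual visits may be used to capture applicable procedures during long-term follow up only". The calendar note adds: "Every attempt should be made to complete the assessments although if they are not completed this is not considered a protocol deviation".
- Section 11.3: "Patients who have progressive disease or start a new treatment are not required come in for clinical follow ups". Sections 6.7.2 and 11.3 allow these patients to be phoned for disease status.

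Nothing in 12.2 or 14.0 links PFS censoring to a scan or to an adequate disease assessment.

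**The concern.** For OS, a contact settles the outcome: the patient is alive. For PFS it does not, because progression is mainly a radiologic finding here. A patient last imaged at one date and last contacted much later stays in the PFS risk set for the whole interval as if known to be free of progression. The error runs one way, and in a single-arm study there is no control curve that shares it. At stake is the Kaplan-Meier PFS curve, a named secondary result, particularly its later part. The two permitted progression dates are a separate looseness in the same section: two analysts could date the same event differently.

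**Working it through.** **1. The only design figure in the plan.** Section 14.0 calls the regimen promising if at least 8 of 28 respond, testing 15% against 35%. Exact binomial: P(X ≥ 8 | 28, 0.35) = 0.818 and P(X ≥ 8 | 28, 0.15) = 0.0486, which match the stated 82% and 5%. PFS does not enter this rule.

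**2. Gap between last imaging and last contact, one patient.** Times are months after the last cycle, with contact at 36.

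- All CTs done: 36 − 24 = 12 months.
- 24-month CT missed: 36 − 12 = 24 months.
- 12- and 24-month CTs missed: 36 − 6 = 30 months.
- No CT after the end-of-treatment scan (30-45 days, about 1 to 1.5 months): about 34.5 to 35 months.

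**3. Effect on the curve (illustrative).** The documents give no expected PFS, no survival after progression and no missed-scan rate, so all three are assumed. The simulation used 600,000 patients per scenario:

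- Time to progression is exponential with median 6 months (3 and 12 also run). Death follows after a further exponential time with median 6 months (3 and 12 also run).
- CT is at cycle 4 day 15 (3 × 21 + 14 = day 77) and cycle 10 day 15 (9 × 21 + 14 = day 203).
- Treatment stops at 17 × 21 = 357 days (11.7 months), or earlier, uniformly from month 1, in 30% of patients.
- The end-of-treatment scan is 37.5 days after stopping. CT follows at +6, +12 and +24 months, and contact at +36.
- The reference has every CT done plus one at +36 months.

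PFS times below are months from enrollment. Reference PFS at median 6 is 38.1% at 12 months, 7.6% at 24 and 1.9% at 36.

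| Follow-up CTs missed | 12-month bias | 24-month PFS, last contact | 24-month bias | 24-month PFS, last assessment |
|---|---|---|---|---|
| 0% | none | 7.6% | none | 7.6% |
| 25% | +0.5 | 8.9% | +1.3 | 8.7% |
| 50% | +1.0 | 10.6% | +3.0 | 10.1% |

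The median does not move in these rows. The zero-missed row follows from the schedule: the reference's extra scan comes no earlier than 1 + 36 = 37 months after enrollment, so the two curves cannot differ before then.

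Other assumptions:

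- Half of progressions found at contacts without CT: 12-month +0.3/+0.5 and 24-month +0.6/+1.3 (25%/50% missed).
- Survival after progression 3 to 12 months, 50% missed: 12-month +0.5 to +1.3, 24-month +1.6 to +4.5.
- Median PFS 3 months: 12-month +0.5/+0.9.
- Median PFS 12 months: 12-month +0.3/+0.7, 24-month +2.0/+4.4.

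For scale, the standard error with 28 patients is √(0.38 × 0.62/28) = 0.092 at 12 months and √(0.076 × 0.924/28) = 0.050 at 24 months.

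**4. How much the censoring date alone corrects at 24 months.** Share removed = (last contact − last assessment)/(last contact − reference).

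- Median 6, 25% missed: (8.9 − 8.7)/(8.9 − 7.6) = 0.2/1.3 = 15%.
- Median 6, 50% missed: (10.6 − 10.1)/(10.6 − 7.6) = 0.5/3.0 = 17%.
- Median 12, 50% missed (a separate run): (31.6 − 29.9)/(31.6 − 27.3) = 1.7/4.3 = 40%.

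The rest of the bias comes from progression that is found late, or only at death, because CTs were missed.

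**5. Dependence on the model.** A simpler model with no deaths gives larger effects. At an assumed median of 13 months, 36-month PFS is 22% (30% of CTs missed) or 31% (60%) under last-contact censoring, and 16% or 15% under last-scan censoring, against a true 15%. Without deaths, nothing else exposes missed progression. The direction agrees; the size, and the share that the date change repairs, do not.

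**The case against.** The strongest case against acting is that the quoted sentence causes little of the bias. With deaths in the model, moving the date recovers 0.2 to 0.5 points at 24 months at median 6, against a standard error of 5. That stands, and it is why the point is minor.

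Three stronger readings are tempting, and the documents do not support them.

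- *CT stopping at 24 of 36 months inflates the curve by itself.* With every CT done there is no bias through month 36. Only about 0.6 of 28 patients would be progression-free at the 24-month CT at median 6 months (4.0 at median 12). A physical examination is scheduled at 36 months and phone contacts ask for disease status, so that time is without imaging, not wholly unassessed.
- *The plan does not say how to treat a death after a long gap.* It does: 12.2.2.2 counts death from any cause, without exception.
- *Events after missed assessments must be censored in the primary analysis.* That rule removes deaths the plan counts, and it can over-correct. With 50% of CTs missed and half of progressions detected, it gives 6.5% at 24 months against a reference of 7.6%, where last contact is 1.3 points too high. In a what-if not drawn from the documents, 30% of patients are assigned to stop early and have no CT after a clean end-of-treatment scan. Last contact then gives 11.2% and the stricter rule 6.3%, against 8.9%: +2.3 becomes −2.6. It belongs in a sensitivity analysis.

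What remains is that contact does not establish freedom from progression, and that a stated rule treats it as if it did.

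**Conclusion.** The point holds as a minor one. The PFS rule borrows the OS censoring date while the plan allows contact without imaging, so unimaged time is credited as progression-free apart from progression found clinically or by phone. At an assumed median PFS of 6 months with 25% or 50% of follow-up CTs missed, the 24-month estimate is about 1.3 or 3.0 points high, and the median is essentially unchanged. Across the death-inclusive runs of random missed CTs at median 6 or 12 months, the 24-month bias ranges from nil to about 4.5 points, below one standard error. These sizes rest on assumed medians, exponential times and missed-scan rates. The direction and the gap arithmetic rest on the plan's own text. A reader might infer that the trial's conclusion is at risk; it is not, because PFS is secondary and descriptive, and the ORR rule, the 28 evaluable patients and the 82% power do not depend on it.

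**What to change.** In 12.2.2.2:

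- (a) Censor patients alive without progression at the last adequate disease assessment that showed no progression. Keep last contact for OS only.
- (b) Use one progression date, the earliest documentation of progression, and delete the scheduled-clinic-visit alternative.
- (c) Keep death from any cause as an event in the primary PFS analysis. Report two sensitivity analyses: last-contact censoring, and censoring at the last adequate assessment of events first recorded after two or more missed scheduled assessments or after the 24-month CT.

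The cost is wording and two extra runs, with no added visits or scans. Censoring comes earlier and the late curve is less precise. Only part of the bias is removed up to 24 months (about 15% to 40% in the cases in step 4). Beyond the last scheduled CT the new rule can read low, because survivors leave the risk set while later deaths still count: with no CT missed, 36-month PFS is 1.45% against 1.87%. The curve should therefore be read only over the imaging period. Neither (a) nor the sensitivity analyses remove bias if missing a scan is related to prognosis.

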12.2.2.3 Overall Survival

The OS is defined as the time from enrollment to the time of death due to any cause. For a patient who is alive at the end of study follow-up, observation of OS is censored on the date of last contact. The distribution of OS will be estimated using the Kaplan-Meier method.

12.2.2.4 Duration of Response

Duration of response (DOR) is defined as the time from first documentation of objective tumor response (CR or PR) to the time to tumor progression or death due

to any cause.

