6.0 TREATMENT PLAN

6.1 Brentuximab Vedotin Administration

Subjects will receive Brentuximab Vedotin 1.8 mg/kg intravenously (IV) once every 3 weeks.

The treatment will be continued until disease progression, unacceptable toxicity, stem cell transplantation or at physician discretion. If a patient has completed 17 cycles, the treating physician can determine if to continue or discontinue treatment in event there is no disease progression or unacceptable toxicity.

CASE 1415

Protocol Version Date: 07/06/2021

Appropriate dose modifications for Brentuximab Vedotin are described in Section 7.0.

For reported adverse events see section 8.0 and potential risks of Brentuximab Vedotin are described in Section 9.0.

No investigational or commercial agents or therapies other than those described below may be administered with the intent to treat the patient's malignancy.

Table 1

| Treatment Regimen | | | | | |
|--------------------------|-----------------------------------|-------------|--------------------|---------------------|---------------------|
| Agent | Pre-medicate / Precautions | Dose | Route | Schedule | Cycle Length |
| Brentuximab Vedotin | None (please see below) | 1.8 mg/kg | IV over 30 minutes | Day 1 of each cycle | 21 days |

All scheduled treatment visits will have a ± 3 -day window due to unanticipated or unavoidable scheduling conflicts except for cycle 1, day 1.

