6.7 Expected Duration of Subject Participation

6.7.1 Duration of Therapy

The treatment will be continued until disease progression, unacceptable toxicity, stem cell transplantation, or at physician discretion. If a patient has completed 17 cycles, the treating physician can determine if to continue or discontinue treatment in event there is no disease progression or unacceptable toxicity.

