12.2.2.5 Time to Treatment Failure

Time to treatment failure (TTF) is defined as the time from enrollment to discontinuation of treatment for any reason, including disease progression, treatment toxicity, and death.

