14.0 STATISTICAL CONSIDERATIONS

Please refer section 12.2 for endpoint definitions. The primary objective is to evaluate overall response rate. For this patient population, response of 15% or less is unacceptable and 35% or more is promising. Twenty-eight evaluable patients will be accrued; if 8 or more patients respond, then the regimen will be considered promising. The significance level of this one-sided test is 5%, and the power is 82%.

Other end points analyzed are CR, PFS, OS, DOR, and TTF. ORR and CR will be estimated using exact 95% confidence intervals. PFS and OS will be estimated using the Kaplan-Meier method. DOR and TTF will be estimated using standard descriptive statistics such as median and range, or mean and standard deviation.

McNemar's test will be used to compare incidence of CD30 positivity via IHC with multi- spectral imaging and RT-PCR to see if different methods result in different findings.

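### PFS and DOR run on through stem cell transplant or new therapy, and no analysis shows how long disease control lasted before it

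*Combined protocol and SAP*

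**What the plan says.** **End of treatment.** Section 6.1 states: "The treatment will be continued until disease progression, unacceptable toxicity, stem cell transplantation or at physician discretion". Section 6.7.1 repeats this, and so does section 11.1.7. The list of reasons for stopping the drug in section 3.2 has treatment completion, progression, adverse events, withdrawal of consent and investigator decision. Transplant is not on it.

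**PFS (12.2.2.2).** PFS is "defined as the time from enrollment into the study to disease progression or death due to any cause". The only censoring rule covers a patient "alive without progression at the end of study follow-up, observation of PFS is censored on the date of last contact".

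**DOR (12.2.2.4).** DOR is "the time from first documentation of objective tumor response (CR or PR) to the time to tumor progression or death due" to any cause. No censoring rule is given.

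**TTF (12.2.2.5).** TTF is the "time from enrollment to discontinuation of treatment for any reason, including disease progression, treatment toxicity, and death".

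**Analysis (14.0).** Kaplan-Meier is assigned to PFS and OS. For the other two: "DOR and TTF will be estimated using standard descriptive statistics such as median and range, or mean and standard deviation". Transplant and later therapy are not mentioned.

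**Follow-up (6.7.2, 11.3).** Patients are followed for 3 years. Those who start a new treatment need not attend the clinic. They can be telephoned about disease status and current lymphoma treatment. The start date of that treatment is not among the listed items.

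**The concern.** The trial is meant to describe what brentuximab vedotin does alone in CD30-low disease. A responder who stops in order to be transplanted, and then stays in remission, goes on accruing DOR and PFS. With no control arm, nothing shows how much of that time belongs to the transplant. The same holds for radiotherapy or any other lymphoma treatment begun before progression. Section 4.2.2 expressly foresees radiotherapy after study treatment ends.

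Two features add to the difficulty. Once a new treatment starts, no protocol scan is required, yet PFS is censored at last contact rather than at the last tumour assessment. And DOR is to be summarised without any method for censored times, so a long post-transplant remission goes straight into a mean or a range.

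At stake is the reading of two secondary endpoints. The go/no-go rule is not involved.

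**Working it through.** **1. The plan's own figures, and whether this point touches them.** With 28 evaluable patients and 8 or more responses required, exact binomial probabilities are:

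- P(X ≥ 8 | n = 28, p = 0.15) = 0.0486, against the stated one-sided 5%.
- P(X ≥ 8 | n = 28, p = 0.35) = 0.818, against the stated 82%.

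Both reproduce. Neither depends on how PFS or DOR is censored.

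**2. How many patients DOR rests on.** Expected responders are 28 × 0.15 = 4.2 and 28 × 0.35 = 9.8. The decision threshold is 8.

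**3. One patient followed through the definitions.** Take a responder who stops for transplant without progression.

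| Endpoint | What happens at transplant |
|---|---|
| TTF | Ends: treatment has been discontinued |
| PFS | Continues to progression, death or last contact |
| DOR | Continues to progression or death; no censoring rule |

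For PFS, the continuation follows from the event definition and the last-contact rule. For DOR, it follows from the event definition and the absence of any other rule.

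**4. Small example (all data assumed).** There are 8 responders. Five progress at 2, 3, 4, 5 and 6 months after response. Three are transplanted at month 3, with the last assessment also taken as month 3, and are in remission when last seen at month 24.

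- *The plan's descriptive method, with 24 months entered as if observed:* median (5 + 6)/2 = 5.5 months; mean (2 + 3 + 4 + 5 + 6 + 3 × 24)/8 = 92/8 = 11.5 months. Post-transplant time supplies 3 × (24 − 3) = 63 of the 92 months.
- *Kaplan-Meier with the clock running (not the plan's DOR method):* 7/8, 6/8, 5/8, 4/8, 3/8. The median is 5 months and the 12-month estimate is 37.5%.
- *Kaplan-Meier censored at transplant:* 0.875, then 0.875 × 6/7 = 0.75; with 3 left at risk, 0.50, 0.25 and 0. The median is 4 months and the 12-month estimate is 0%.

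The example shows direction. The fall from 37.5% to 0% follows from the chosen inputs.

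**5. Range under assumed inputs.** Large-sample simulation with exponential times. Of responders, 20% to 50% are selected for transplant at random, and those still in response at 3 months receive it. Median post-transplant remission is 12 to 24 months, and everyone is followed to the event.

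| Assumed drug-only median DOR (months) | Responders actually transplanted | Median, clock running | Median, Kaplan-Meier censored | Mean, drug only | Mean, clock running |
|---|---|---|---|---|---|
| 4 | 12% to 30% | 4.2 to 4.8 | 4.0 | 5.8 | 7.2 to 14.3 |
| 6 | 14% to 35% | 6.4 to 8.1 | 6.0 | about 8.7 | 9.9 to 17.8 |
| 9 | 16% to 40% | 9.4 to 12.2 | 9.0 to 9.1 | 13.0 | 13.7 to 21.6 |

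With no transplants the difference is zero. The median moves modestly; the mean, which section 14 allows, can move a great deal. Censoring recovers the drug-only median here only because selection was random. In practice it will not be.

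**The case against.** The strongest reply is that following patients through later therapy is a legitimate treatment-policy choice, and that the proposed alternative has a known flaw: patients chosen for transplant differ from the rest, so censoring them is informative. That stands. It is why the present definitions should remain the main analysis. It does not answer the gap: the plan does not label the choice, gives no supportive analysis and does not count the patients affected.

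Other objections also stand in part. The documents give no transplant rate, and do not say that responders are likelier to be transplanted, so the size is assumed. PFS and DOR are untested secondary summaries.

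Three stronger readings are tempting and are not supported:

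- A reader might infer that TTF contradicts DOR for the patients who do best. It does not: TTF measures time to stopping treatment and DOR measures time to progression or death, so different values for one patient are expected. The narrower point is that TTF pools transplant in remission with failure, so it does not supply the missing single-agent duration.
- A reader might infer that the plan sets out to credit brentuximab with post-transplant remission. No section says so; that is a consequence of the definitions in a single-arm trial.
- A reader might take a 12-month DOR estimate or a DOR curve as the plan's output. Section 14 plans neither.

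**Conclusion.** The point holds as a gap in the analysis of two secondary endpoints. As written, PFS and DOR include remission after transplant or other therapy begun without progression, and nothing planned shows the time before it.

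The documents do not let the size be calculated. It is nil if no patient takes that route. With 4 to 10 responders, a few such patients can shift the DOR summary, and under the assumed inputs above the mean shifts much more than the median. ORR, CR rate, OS, sample size and power do not change. This is a worthwhile, inexpensive improvement, not a flaw in the trial's main conclusion.

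**What to change.** Keep the current PFS and DOR definitions as the main analysis and add to section 14:

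> DOR is estimated by Kaplan-Meier. As a supportive analysis, PFS and DOR are also estimated by Kaplan-Meier with censoring at the last tumour assessment before stem cell transplant, radiotherapy or other anti-lymphoma therapy started without progression; the number of patients so censored is reported. TTF events are tabulated by reason, with transplant in remission shown separately.

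Reconcile the stopping reasons in section 3.2 with those in sections 6.1, 6.7.1 and 11.1.7, so that transplant is recorded as a discontinuation reason of its own. In sections 6.7.2 and 11.3, add the start date of any new lymphoma therapy to the items collected.

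**Cost.** One extra analysis and two small additions to data capture. The second curve will usually be shorter, and its censoring is informative, so it must stay supportive. It will also be coarse. On-treatment scans fall at cycle 4 day 15 (3 × 21 + 15 = day 78) and cycle 10 day 15 (9 × 21 + 15 = day 204), which is 126 days apart. A responder transplanted soon after the first scan may therefore be censored close to the response date, unless the end-of-treatment scan comes before transplant.
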